2.1.2 PrEP Comparison Component Study Design

The IMPAACT 2009 PrEP Comparison Component is a parallel observational cohort study. It will assess feasibility, acceptability, adherence to, and safety of PrEP during pregnancy and in the postpartum period among adolescents and young women who are HIV-negative. Women will be screened prior to 32 weeks' gestation and subsequently enrolled in two cohorts: those who choose to initiate PrEP at enrollment (Cohort 1) and those who decline (Cohort 2). Infants will be enrolled *in utero* at the same time the woman is enrolled. A randomized trial in which women were assigned to an arm that would not receive PrEP would be unethical at this time due to the overwhelming evidence supporting the efficacy of PrEP to prevent HIV infection. All women enrolled in the study will receive a standard of care package of HIV prevention services and a study-specific behavioral risk reduction intervention. Additionally, all women will receive support for antenatal, delivery and early infant care through brief motivational-interviewing informed counseling at each study visit and one-way mHealth messaging services. Women who choose to initiate PrEP will be provided PrEP as well as drug-level informed adherence support intervention.

Approximately 350 women will be enrolled to achieve at least 300 evaluable women (200 in Cohort 1 and 100 in Cohort 2) and their infants, defined as completing the week 26 postpartum visit. Women will be accrued over a 12-month period (from the date of first enrollment) and followed through 26 weeks postpartum. For each woman, the duration of follow-up is expected to range from seven to 12 months depending on gestational age at entry. For each infant, the expected duration of follow-up is approximately six months.

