6.3.2 Second Primary Estimand

Primary Objective 2: To assess the safety of FTC/TDF for PrEP during pregnancy and postpartum by comparing pregnancy outcomes and maternal and infant safety between cohorts.	
Estimand description	Incidence rate ratio of cumulative adverse events (AEs) up to 26 weeks postpartum among PrEP exposed vs. PrEP unexposed women
Treatment	
 1. Daily oral PrEP (200 mg FTC/ 300 mg TDF) throughout follow-up. 2. Enhanced adherence support, including SMS messaging and feedback of drug levels with tailored counseling. 3. Behavioral HIV risk reduction package
Target population	Analysis set
Women who are pregnant and HIV-uninfected, 16-24 years of age, with a confirmed singleton pregnancy of 32 weeks' gestation or less and who have access to a mobile phone and are able to receive and read SMS messages	Maternal Safety Set: all enrolled maternal participants
Variable(s)	Outcome measure(s)
Occurrence of at least one of the following maternal AEs up to 26 weeks postpartum 
 • Grade 3 or higher adverse events • Grade 2 or higher chemistry abnormalities 	Outcome measures as defined by the variables (graded according to the NIAID DAIDS Table for Grading the Severity of Adult and Pediatric Adverse Events). 
 • The start of person-time for the PrEP-exposed group is study entry for Cohort 1 and Cohort 2/Step 2 entry for Cohort 2; • The start of person-time for the PrEP unexposed group is study entry (for Cohort 2 only; person-time is censored when initiating PrEP for participants enrolled in Cohort 2/Step 2)
Handling of intercurrent events	Handling of missing data

 • Failure to start PrEP (in Cohort 1 or Cohort 2/Step 2) (Treatment policy strategy) • Premature discontinuation of PrEP (Treatment policy strategy) 	Participants who discontinue follow-up before the 26-week postpartum visit will have their outcome determined based on data available until the time of discontinuation (i.e., a participant who discontinued follow-up without a prior AE is assumed not to have an AE had they been observed for the intended duration).
Population-level summary measure	Analysis approach

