Incidence rate ratio (among PrEP exposed vs. PrEP unexposed women) of cumulative adverse events up to 26 weeks postpartum	Incidence rate ratio of cumulative AEs up to the week-26 postpartum visit (among PrEP exposed vs. PrEP unexposed women) estimated based on Poisson distribution (with 95% Wald CI).

Supplemental Analyses:

- Analyses will be repeated stratified by time period (i.e., antepartum (AP) and postpartum (PP), and within AP stratified by gestational age category of enrollment).
- Rates of maternal adverse events in AP and PP periods will also be calculated and compared across levels of PrEP adherence (based on TFV-DP levels in dried blood spots). Models will be fit adjusting for potential confounders.

- To compare time to first adverse event in PrEP exposed vs. PrEP unexposed women, the hazard ratio (95% CI) will be estimated with Logrank test p-value from Cox proportional hazards regression on time to first AE with PrEP exposure as a time-varying covariate.

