
 • Incidence rate ratio (among PrEP exposed vs. PrEP unexposed infants) of cumulative adverse events up to the age 26-week visit 	
 • Incidence rate ratio of cumulative adverse events up to the age 26-week visit (among PrEP exposed vs. PrEP unexposed infants) estimated based on Poisson distribution (with 95% Wald CI).

Supplemental Analyses:

- Analyses will be repeated stratifying by time of infant drug exposure (i.e., antepartum (AP) and postpartum (PP), and within AP stratified by gestational age category of maternal enrollment).
- Rates of infant adverse events will also be calculated and compared across levels of maternal PrEP adherence (based on TFV-DP levels in dried blood spots). Models will be fit adjusting for potential confounders.
- To compare time to first infant adverse event in PrEP exposed vs. PrEP unexposed infants, the hazard ratio (95% CI) will be estimated with Logrank test p-value from Cox proportional hazards regression on time to first AE with PrEP exposure as a time-varying covariate.

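### SAP 6.3.2 pairs a first-event variable with a Poisson rate ratio of cumulative AEs and a drop-out gloss suited to a fixed-period risk; 6.3.4 repeats the ratio and the gloss

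*SAP*

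**What the plan says.** SAP 6.3.2 (maternal AEs) has five relevant elements.

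- **Variable:** "Occurrence of at least one of the following maternal AEs up to 26 weeks postpartum", covering Grade 3 or higher AEs and Grade 2 or higher chemistry abnormalities. The outcome-measure cell refers back to this variable.
- **Summary and analysis:** "Incidence rate ratio of cumulative AEs up to the week-26 postpartum visit", by a Poisson model with a 95% Wald interval.
- **Person-time:** it starts at study entry, or at Step 2 entry for exposed time in Cohort 2. For unexposed time, "person-time is censored when initiating PrEP for participants enrolled in Cohort 2/Step 2".
- **Drop-outs:** women who leave early "will have their outcome determined based on data available until the time of discontinuation". An i.e. clause then adds that "a participant who discontinued follow-up without a prior AE is assumed not to have an AE had they been observed for the intended duration".
- **Supplement:** "Cox proportional hazards regression on time to first AE with PrEP exposure as a time-varying covariate".

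SAP 6.3.4 (infant AEs) has the same rate ratio, again "estimated based on Poisson distribution (with 95% Wald CI"), the same drop-out sentence with its gloss, and the same supplemental Cox model. Its variable lists infant death and Grade 3 or higher AEs and has no at-least-one wording.

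On follow-up, SAP 2.1.2 says that for each woman "the duration of follow-up is expected to range from seven to 12 months depending on gestational age at entry"; for each infant it gives approximately six months. Protocol 9.2.6 (Primary Objective 2.3.2) also plans to compare cumulative AE rates, and names Cox regression for this.

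**The concern.** A statistician given SAP 6.3.2 could compute any of three quantities and cite the table for each: a rate of first AEs with time stopped at the event, a rate of all AEs over all observed time, or women with any AE divided by full person-time. They have different estimates or different correct variances.

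The gloss adds a second conflict. In a person-time rate, time after drop-out simply leaves the denominator, so nothing need be assumed about it. Assuming that a leaver would have stayed AE-free to the end is how one completes a yes/no outcome over a fixed period. One half of the drop-out sentence therefore fits the estimator and the other half does not.

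These are the primary maternal and infant AE results of a non-randomised safety comparison. For women, planned follow-up varies from seven to 12 months, so a risk and a rate are not interchangeable. First versus all events is part of the estimand, and SAP 1.1 assigns the primary estimands to this SAP. If the choice is left open, it can be made after the data are seen.

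**Working it through.** **Inputs.** 200 evaluable women in Cohort 1 and 100 in Cohort 2, about 15% attrition, and the six pairs of event proportions in Table 10 (all Protocol 9.2.4). Frailty variances, AEs per woman and loss by cohort are not in the documents and are assumed below.

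**The plan's own figure.** The Table 10 example is 10% vs 23%, 80% power, alpha 0.05. A two-sided pooled test of two proportions without continuity correction gives power 0.806 and a Cohort 2 size of 99, so it reproduces. The rounded 15%/29% and 20%/35% rows give 0.780 and 0.778; with the printed odds ratios, all six rows give 0.793 to 0.801. Table 10 therefore sizes a comparison of proportions with an event and says nothing on power for an all-event rate ratio.

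**Reading (a): all AEs counted, plain Wald interval.** Standard error of the log ratio: √(1/e₁ + 1/e₀), where e₁ and e₀ are event totals. If AE counts vary between women with gamma frailty variance v and mean m, then variance/mean = 1 + m·v, while plain Poisson assumes 1. At m = 0.25 and v = 4 this is 1 + 0.25 × 4 = 2.0. Coverage with no true effect, 40,000 simulated trials per setting:

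| AEs per woman | v = 0.5 | v = 1 | v = 2 | v = 4 |
|---|---|---|---|---|
| 0.10 | 95.4% | 95.0% | 93.6% | 91.6% |
| 0.25 | 93.6% | 92.4% | 89.7% | 84.0% |

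A variance robust to clustering by participant gives about 94% to 95%, with intervals 2% to 35% wider for v from 1 to 4.

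**Reading (b): women with at least one AE, divided by full person-time.** With equal follow-up this returns the risk ratio p₁/p₀. Under a constant hazard the first-event rate ratio is ln(1 − p₁)/ln(1 − p₀). For 10% vs 23%: 0.23/0.10 = 2.30 against ln(0.77)/ln(0.90) = 2.48, which is 7% low.

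| Cohort 2 / Cohort 1 | Risk ratio | Rate ratio | Shortfall |
|---|---|---|---|
| 2% / 10.5% | 5.25 | 5.49 | 4% |
| 5% / 15.6% | 3.12 | 3.31 | 6% |
| 10% / 23% | 2.30 | 2.48 | 7% |
| 15% / 29% | 1.93 | 2.11 | 8% |
| 20% / 35% | 1.75 | 1.93 | 9% |
| 25% / 41% | 1.64 | 1.83 | 11% |

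The Poisson interval is 1% to 18% too wide for the risk ratio, but its coverage of the rate ratio stays at 95% to 96%.

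**Reading (c): the gloss used to credit drop-outs with unobserved time.** Assume exits fall on average at mid-period. A group losing a fraction d is then observed for 1 − d/2 of the time credited to it. With a true ratio of 1:

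- 10% exposed, 25% unexposed: (1 − 0.05)/(1 − 0.125) = 0.950/0.875 = 1.09
- 25% exposed, 10% unexposed: 0.875/0.950 = 0.92
- 15% in both: 0.925/0.925 = 1.00

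Person-time to the actual exit gives 1.00 in each case.

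**The case against.** The strongest reply is that 6.3.2 is less open than it looks. The variable is occurrence of at least one AE, the outcome cell points back to it, and the drop-out sentence turns on having no prior AE. Together these indicate first events, and cumulative may just mean accrued over the period. On that reading (a) does not arise. This stands in large part: a reader might infer that the plan says nothing about the numerator, and for 6.3.2 that goes too far. What remains is that the analysis row is worded for cumulative AEs and nothing stops person-time at the first one. At least one of the listed items could also mean either type of AE, which would leave first versus all unsettled. In 6.3.4 only the no-prior-AE phrase hints at first events.

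Second, the gloss need not change any person-time. The operative clause is ordinary censoring, and no text credits a leaver with time not observed. A reader might infer that the gloss biases the result; that needs this extra step plus unequal loss, and the documents give only overall attrition. This objection stands on size. It does not make the gloss fit the estimator.

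Third, the seven-to-12-month argument is maternal. Extending it to 6.3.4 is not supported, because infant follow-up is about six months for all.

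Fourth, the supplemental Cox models give a defined first-event estimate. That is real but partial mitigation, since they are not the primary measure.

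Fifth, offset coding, the counting of persistent abnormalities and re-entry at Step 2 may be in the Analysis Implementation Plan, which was not available. Their absence from the SAP is not counted as a fault here. Nor is the choice of a cumulative rate, which Protocol 9.2.6 also names.

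**Conclusion.** The point holds as an internal inconsistency in the wording of two primary safety estimands, and confidence in that is high. It should be corrected. It is not a demonstrated bias.

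The three sizes belong to mutually exclusive readings or to added assumptions and must not be summed. Under (a), coverage is near nominal at 0.10 AEs per woman with frailty variance up to 1; the 84% figure needs both 0.25 AEs per woman and an assumed variance of 4. Under (b), the 4% to 11% shortfall assumes constant hazard and equal follow-up, and Protocol 9.2.4 expects low rates, which puts it at the small end. Under (c), the shift of about 8% to 9% either way rests on an assumed 10%/25% split in loss and vanishes when loss is equal. The conflict is clearest in 6.3.2; in 6.3.4 the gloss conflicts equally with the estimator, and the numerator is less determined.

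**What to change.** Make three changes in both SAP 6.3.2 and 6.3.4:

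1. Delete the i.e. clause from the drop-out cell and keep the part that uses data up to discontinuation.
2. State that person-time ends at last contact, at the Week 26 visit, or, for unexposed time, at PrEP start.
3. Name one numerator. Either count the first qualifying AE and end person-time at that AE, which matches the at-least-one variable in 6.3.2; or count all AEs, reword that variable, and use a participant-clustered robust or negative binomial variance. Either is coherent once stated.

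Offset coding, how a persistent abnormality is counted, and whether a Cohort 2 participant with an AE before Step 2 re-enters as exposed can go in the Analysis Implementation Plan.

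The cost is SAP wording only, with no new data or visits. With the first-event choice, repeat AEs leave the primary result. With the all-event choice, the interval widens by up to about 35% in the assumed scenarios.

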### **1.5 Hypotheses for the PrEP Comparison Component**

- At least 75% of women who opt to initiate PrEP will achieve a high level of adherence throughout pregnancy, as measured by adequate TFV-DP concentrations in DBS specimens.
- The rate of maternal and infant adverse events (including adverse pregnancy outcomes) will be higher among mother-infant pairs in which the mother initiates PrEP during pregnancy than in pairs in which the mother declines PrEP.
- The mean bone mineral density for the lumbar spine and hip at baseline and at Week 26 postpartum will be lower among women who initiated PrEP during pregnancy than among women who decline PrEP.

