## 3.2 PrEP Comparison Component Study Design

The PrEP Comparison Component will assess feasibility, acceptability, adherence to, and safety of PrEP during pregnancy and postpartum in HIV-uninfected adolescents and young women. Women will be enrolled prior to 32 weeks' gestation in two cohorts: those who agree to initiate PrEP (Cohort 1) and those who decline (Cohort 2). Infants will be enrolled *in utero* at the same time the woman is enrolled. A randomized trial in which one arm would not receive PrEP would be unethical at this time due to the overwhelming evidence supporting the efficacy of PrEP to prevent HIV infection (172). All women enrolled in the study will receive a standard of care package of HIV prevention services and a study-specific behavioral risk reduction intervention. Additionally, all women will receive support for antenatal, delivery and early infant care through

one-way mHealth messaging services. Women who choose to initiate PrEP will be provided PrEP as well as a study-specific adherence support intervention.

Regardless of cohort, all maternal participants will follow similar schedules of evaluations through the course of pregnancy and in the 26 weeks following delivery. Following Cohort 2 provides an opportunity to document the process of decision-making around HIV prevention during this time of substantial risk; as these women may choose to initiate PrEP at any stage following study entry, triggers for change in PrEP perceptions and acceptability over time will be recorded to better understand women's motivation to seek additional HIV prevention (see [Section 3.2.1](#)) services. As Cohort 2 is not exposed to antiretroviral agents during pregnancy or postpartum, the study will also obtain preliminary safety data for TDF use in HIV-uninfected women during this period. Cohort 2 will serve as a comparison group for estimates of incidence and prevalence of maternal and infant safety outcomes including a) pregnancy outcomes, b) maternal adverse events, and c) infant growth and development between the two cohorts (see [Section 9.2.2](#)). The primary analysis will be based on original Cohort designation at baseline. Additional secondary analyses that consider the population of women who may initially decline PrEP and then later decide to initiate it will be considered, refer to [Section 9](#).

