## 9.2 PrEP Comparison Component

Primary outcome measures listed below will be addressed in the study's primary Statistical Analysis Plan, which will define the content of the Primary Analysis Report. This report will form the basis for the primary study manuscript and results reporting to ClinicalTrials.gov. Outcomes of interest for additional objectives intended for subsequent publications are listed under "Other" and "Exploratory" Outcome Measures.

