Regardless of cohort, all maternal participants will follow similar schedules of evaluations through the course of pregnancy and in the 26 weeks following delivery. Women in Cohort 2 may choose to initiate PrEP at any stage following study entry, and triggers for change in PrEP perceptions and acceptability over time will be recorded to better understand women's motivation to seek additional HIV prevention services. As Cohort 2 is not exposed to antiretroviral agents during pregnancy or postpartum, its unexposed time period will serve as a comparison group for estimates of incidence and prevalence of maternal and infant safety outcomes including a) pregnancy outcomes, b) maternal adverse events, and c) infant growth and development between the two exposure groups.

The primary objectives focus on women who initiate PrEP during pregnancy and continue through the first 26 weeks postpartum (Cohort 1). Adherence to PrEP will be assessed by measuring TFV-DP drug levels in dried blood spots. Participants in this arm will receive an intervention designed to provide participant-centered support, including support for PrEP use/adherence, comprised of a) two-way SMS messaging related to PrEP adherence, and b) targeted adherence counseling guided by TFV-DP drug levels.

Maternal participants who change their intent regarding PrEP will be allowed to do so. Participants in Cohort 1 who choose to stop PrEP will continue in follow-up. Maternal participants

in Cohort 2 who subsequently choose to initiate PrEP will undergo a Step Change, and will be referred to as Cohort 2/Step 2 and will follow the procedures for Cohort 1/Cohort 2 Step 2. While a formal step change will only be required when those originally declining PrEP later chose to initiate it, there is no upper limit set on the number of switches allowed for each participant. Switching will be closely monitored as part of feasibility and adherence outcomes.

There will be no randomization for this study. To monitor the balance of the maternal participants enrolled among various groups, the enrollment will be stratified by:

- Cohort: PrEP vs. No PrEP at enrollment
- Trimester of enrollment during pregnancy: 1st or 2nd trimester vs. 3rd trimester
- Country
- Age at enrollment: 16-17 years vs. 18 years of age and older

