2.2.2 Hypotheses for the PrEP Comparison Component

1. At least 75% of women who opt to initiate PrEP will achieve a high level of adherence throughout pregnancy, as measured by optimal TFV-DP concentrations in DBS specimens.
2. The rate of maternal and infant adverse events (including adverse pregnancy outcomes) will be higher among mother-infant pairs in which the mother initiates PrEP during pregnancy or postpartum than in pairs in which the mother declines PrEP.

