2.3.3 Primary Study Objectives for PrEP Comparison Component

This Primary SAP addresses the following primary objectives in the study protocol. Other study objectives in the protocol will be addressed in subsequent analysis plans.

- To characterize PrEP adherence among HIV-uninfected young women during pregnancy and for twenty-six weeks postpartum, when provided with enhanced adherence support through mobile technology and counseling based on observed drug levels.
- To assess the safety of FTC/TDF for PrEP during pregnancy and postpartum by comparing pregnancy outcomes and maternal and infant safety between PrEP-exposed and PrEP unexposed groups.

The Primary SAP includes objectives, estimands and outcome measures to be addressed in the primary analysis report for the PrEP Comparison Component. The analysis or monitoring reports prepared by the SDMC for IMPAACT 2009 will include monthly monitoring reports, annual and ad hoc SMC reports, and a final report to be prepared after all participants have completed their last follow up visit.

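### The SAP makes PrEP exposure the primary safety contrast without recording the departure from the protocol's original-cohort rule, and names no covariates for the primary rate ratios or infant mean comparisons

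*SAP*

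**What the plan says.** **Grouping.** Protocol 3.2 states: "The primary analysis will be based on original Cohort designation at baseline". Analyses that deal with women who first decline and later start PrEP are called secondary. The same section says "Cohort 2 will serve as a comparison group for estimates of incidence and prevalence of maternal and infant safety outcomes". SAP 2.1.2 rewrites that sentence so that, for Cohort 2, "its unexposed time period will serve as a comparison group for estimates of incidence and prevalence of maternal and infant safety outcomes". The hypothesis changes too. Protocol 1.5 concerns pairs "in which the mother initiates PrEP during pregnancy than in pairs in which the mother declines PrEP"; SAP 2.2.2 concerns pairs "in which the mother initiates PrEP during pregnancy or postpartum than in pairs in which the mother declines PrEP". SAP 2.3.3 words the safety objective as "comparing pregnancy outcomes and maternal and infant safety between PrEP-exposed and PrEP unexposed groups".

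In 6.3.2 and 6.3.4, Cohort 2 participants move into the exposed group from Step 2 entry, and their unexposed person-time is censored when PrEP starts. In 6.3.5, infants exposed before the measurement count as exposed.

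**Adjustment.** Protocol 9.2.1 says that women choose their own cohort, that confounders may therefore be unevenly distributed, and that they will be measured and adjusted for. Its example is a serodiscordant partnership. It also warns that small numbers will limit how many confounders can be fitted. The primary analysis in SAP 6.3.2 is "Incidence rate ratio of cumulative AEs up to the week-26 postpartum visit (among PrEP exposed vs. PrEP unexposed women) estimated based on Poisson distribution". Section 6.3.4 has the same form for infants, and 6.3.5 uses t-tests or Wilcoxon tests.

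**The concern.** Safety is the second primary objective. Someone holding both documents cannot tell whether the protocol's primary grouping was dropped on purpose, and no original-cohort safety result is planned against which to judge the change.

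The headline comparisons in 6.3.2, 6.3.4 and 6.3.5 are also crude comparisons of self-selected groups. Balance by country, age group and trimester is managed during accrual (Protocol 9.2.3 and 9.2.5, SAP 2.1.2). Partner HIV status, which the protocol itself offers as the likely confounder, is not managed. Partner characteristics are only compared descriptively at entry (Protocol 9.2.6, SAP 5). A crude primary estimate could therefore show, or hide, a difference that PrEP did not cause.

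**Working it through.** **1. Grouping, side by side.**
- Protocol 3.2, objective 2.3.2 and the adverse-event and infant-mean paragraphs of 9.2.6 compare Cohort 1 with Cohort 2.
- SAP 2.3.3 and 6.3.2 to 6.3.5 compare exposed with unexposed. The objective line heading each of the four safety tables still compares cohorts.
- The SAP lists no original-cohort safety estimate, even as a sensitivity analysis.
- Only Cohort 2 women who switch (and their infants) change group. Under the treatment policy strategy, Cohort 1 women who stop or never start stay exposed. Section 6.3.5 conflicts with this: it classes infants of women who never used PrEP as unexposed.

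**2. Adjustment, by estimand.**
- 6.3.2 and 6.3.4: primary Poisson rate ratio, no covariates named. One supplemental sentence on adjusting for confounders sits in the bullet on adherence levels.
- 6.3.3: a supplemental multivariable logistic model. The primary analysis cell is not readable.
- 6.3.5: primary t-test or Wilcoxon test, no adjusted analysis listed. Protocol 9.2.6 also plans unadjusted t-tests here.

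**3. The protocol's figure.** Table 10 gives 80% power for 10% (n = 100) against 23% (n = 200), two-sided 0.05 assumed. Power = Φ[(d − 1.96·SE0)/SE1].
- Pooled risk = (46 + 10)/300 = 0.187
- SE0 = √(0.187 × 0.813 × 0.015) = 0.0477
- SE1 = √(0.23 × 0.77/200 + 0.10 × 0.90/100) = 0.0423
- Power = Φ[(0.13 − 0.0935)/0.0423] = 80.6%

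The figure reproduces, as an unadjusted comparison by cohort.

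**4. What the grouping does.** The documents give no switching rate, so these are illustrations.
- *Power.* Assume each switcher carries half the excess risk, 0.10 + 0.065 = 0.165. At 10% switching, original cohort compares 0.23 with 0.10 + 0.1 × 0.065 = 0.1065 (200 against 100): 75.5%. Exposure grouping compares (46 + 10 × 0.165)/210 = 0.227 with 0.10 (210 against 90): 76.0%. At 30% switching the same formulas give 64.0% and 63.8%. Power does not decide between the contrasts.
- *Bias with no effect, 6.3.3 composite.* A woman must still be pregnant to switch, so early deliveries stay in the unexposed group. A simulation assumed entry uniform over 12 to 32 weeks, delivery normal with mean 39.2 weeks and 13% before 37, 12% small for gestational age, and a constant switching hazard. Exposure grouping gave an odds ratio of 0.99 at 5% switching, 0.98 at 10% and 0.96 to 0.97 at 16%.
- *Dilution with a true effect.* If PrEP doubles the weekly preterm hazard, the odds ratio is 1.63 without switching. At 16% switching it is 1.53 by original cohort and 1.58 by exposure.
- *Rate ratio in 6.3.2.* With no effect it is 1.00 if the event rate is constant over time, and 0.95 to 1.04 at 16% switching in pregnancy if pregnancy and postpartum rates differ twofold.

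**5. What omitting adjustment does.** Assume no PrEP effect, 25% risk without an HIV-positive partner, and such partners in 10% of Cohort 2 and 20% of Cohort 1.
- *Odds doubled* (0.333 to 0.667, risk 40%). Cohort 1: 0.2 × 0.40 + 0.8 × 0.25 = 0.280. Cohort 2: 0.1 × 0.40 + 0.9 × 0.25 = 0.265. Crude OR = (0.280/0.720)/(0.265/0.735) = 1.08; false-positive rate 5.9%.
- *Wider range.* With 30% in Cohort 1 the OR is 1.16. With the odds tripled it is 1.13 at 20% and 1.27 at 30% (false-positive rate 14.3%).
- *Rate ratio* (6.3.2, 6.3.4; equal follow-up, no switching), event rate doubled: (1 + 0.2)/(1 + 0.1) = 1.09.
- *Infant whole-body bone mineral content* (6.3.5), 5 percentage points more of Cohort 1 in a country whose mean differs by 0.5 SD: 0.05 × 0.5 × 16.6 = 0.4 g, against SE = 16.6 × √(1/200 + 1/100) = 2.03 g.

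**The case against.** The strongest reply is that the protocol is itself mixed. Section 9.2.6 models PrEP use for pregnancy outcomes, 9.3.3 pools Cohort 1 with Cohort 2/Step 2 in its safety triggers, and 9.2 leaves it to the SAP, "which will define the content of the Primary Analysis Report". This stands as far as it goes: an exposure contrast is defensible. It does not excuse leaving a departure from a stated primary basis unrecorded.

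On adjustment, a reader might infer that the SAP has none. That is wrong: supplemental adjusted models are listed for pregnancy outcomes and, briefly, for maternal and infant adverse events. Nor does Protocol 9.2.1 say that the primary estimate itself must be adjusted, and 6.3.5 follows the protocol's own tests. A reader might also take the primary odds ratio in 6.3.3 to be crude, or the exposure rule there to be missing. Cells of that table are not readable, so neither can be asserted.

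Further detail may sit in the Analysis Implementation Plan, which is not available. However, SAP 1.1 describes that plan as table outlines and coding, and assigns the analytic approach for primary estimands to the SAP.

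Finally, country balance is actively managed and Cohort 2 women must express unwillingness to take PrEP at entry (Protocol 4.2.1.11). Large country imbalance or heavy switching should therefore not be presumed.

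**Conclusion.** The point stands as an unrecorded change of primary contrast, together with primary safety analyses in 6.3.2, 6.3.4 and 6.3.5 that name no covariates. It should be fixed before analysis.

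A reader might infer that the safety results would be seriously biased. The documents do not support that: they give no imbalance or switching rates. Under modest assumptions the distortions are small (crude odds ratio about 1.08; null odds ratio 0.98 to 0.99 at 5 to 10% switching), well below the smallest odds ratio in Table 10 (2.10). Larger figures, such as 1.27, need both a strong confounder and a wide imbalance in partner status. The case for change rests on the mismatch between the documents, on the confounder the protocol names, and on the low cost of repair.

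**What to change.** 1. **Adjust.** For 6.3.2 to 6.3.5, make the main estimate an exposed-versus-unexposed comparison adjusted for country, age group, gestational age at entry and partner HIV status (positive, negative, unknown), with the crude estimate alongside. Partner status is already collected by CASI. Keep the unknown level, because Protocol 1.3.1 cites South African reports that only 40% of recently pregnant women knew their partner's status. In 6.3.2 add pregnancy/postpartum period.
2. **Set model size in advance.** Use expected, not observed, event counts to fix which outcomes take a reduced set or a propensity score. With four countries assumed, as in the PK Component, the model has 1 + 3 + 1 + 1 + 2 = 8 parameters. A 25% outcome gives 75/8 = 9.4 events per parameter; a 10% outcome gives 30/8 = 3.8, or 30/2 = 15 with a score. The PrEP-initiation model in Protocol 9.2.6, which SAP 5 does not carry over, could supply the score, but an entry-based score does not describe later Step 2 initiation.
3. **Declare the contrast.** If exposure stays primary, say that it replaces the rule in Protocol 3.2, correct the objective line in the four tables, and add the original-cohort contrast as a prespecified sensitivity analysis.
4. **Reconcile 6.3.5.** State whether infants of Cohort 1 mothers who never start PrEP count as exposed.

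**Cost.** SAP wording and a few model terms on data already collected. In simulation with balanced covariates the standard error of the log odds ratio rose from 0.286 to 0.296, about 3.5%. Some confounding will remain because partner status is self-reported, and each outcome will carry two contrasts.
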